### 1.1. Study objectives and endpoints

4-Mar-2022

The aim of this study is to assess the effectiveness of Almega®PL on improving blood markers associated with heart health of iwi customers. Specifically, we would like to confirm the decrease in cholesterol observed in our previous trial (Rao et al., 2020) while assessing the capacity to also decrease triglycerides (primary outcome). As a secondary objective we would like to understand if EPA, precursor of signalling molecules involved in the inflammatory response, could help decrease the inflammatory marker hs-CRP.

Objectives and related endpoints are described in Table 1-1 below

Table 1.1-1. Objectives and relative endpoint

| OBJECTIVES   | ENDPOINTS   | JUSTIFICATION FOR ENDPOINTS   |
|--|---|---|
| Primary  |   |   |
| Can Almega® PL
supplement decrease
triacylglycerides in a
generally healthy
population?  | Triglyceride change from baseline over 6-month period.  | Triglyceride levels is an
atherogenic lipid and an
important risk factor in
cardiovascular disease   |
| Secondary  |   |   |
| Can Almega® PL supplement replicate the decrease in VLDL and total cholesterol we observed in our previous clinical trial (Rao et al., 2020)? Will the results from a controlled population translate to the iwi costumers? Can Almega® PL | Total Cholesterol change from baseline over 6-month period. VLDL-Cholesterol change from baseline over 6-month period. LDL-Cholesterol change from baseline over 6-month period. HDL-Cholesterol change from baseline over 6-month period. hs-CRP change from baseline over 6-month period. Fasting glucose change from baseline over 6-month period. HbA1c change from baseline over 6-month period. | Cholesterol in plasma levels is atherogenic and a risk factor in cardiovascular disease. Hs-CRP is an age-related inflammatory market. Omega-3 help regulate the inflammatory response. |

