8.3 Background

AlmegaPI was previously studies in a double-blind, placebo-controlled, randomized three-month clinical trial (Rao et al., 2020 *Nutrients*, 12, 1869) that showed that this product decreases total cholesterol and VLDL-cholesterol.

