Along with the fist supplement order shipped to the new subscriptions, participants will receive the baseline hearth health test kit from ImawareTM. Participants will be contacted 3 and 6 months after and they will be sent subsequent kits once the confirmed adherence to the supplement. The test kits will monitor blood lipid levels across a supplementation period (baseline, month 3 and month 6) thanks to a finger prick blood drawing system. The age, height, weight, gender, fasting total cholesterol, LDL-cholesterol, HDL-cholesterol, calculated VLDL-cholesterol, triglycerides, as well as hs-CRP inflammatory marker, and glucose and HbA1c as diabetes indicator of each participant will be recorded over the study period. **Qualitas Health** will receive the aggregated data of the participants only for statistical analyses at their headquarter in Houston and store it in the company share drive with access restricted to those involved in the study. There will be no cost incurred for this analytical assessment to the participant.

Results for the per intended-to-treat (ITT) population will be first tested for normality before any other test will be conducted and baseline data was compared against month 3 and month 6 data. Based on the distribution of data, either Welch two-sample unequal variance t-tests or Wilcoxon Ranks sum tests will be used to compare two-tailed differences between groups. Differences will be considered statistically significant at a p value < 0.05, but the thresholds for the significance of the 20 clinical outcomes were adjusted for multiple variables by the Bonferroni adjustment method which decrease the significance of p-value from <0.05, down to <0.0025. Intervention

effect will also test using an analysis of covariance model (ANCOVA) adjusting for baseline parameters.

[figure not shown]

Figure 1-1 Study design

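### The aim to confirm and replicate the earlier VLDL and total-cholesterol decrease claims more than an uncontrolled change, with a calculated VLDL, can support

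*SAP*

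**What the plan says.** The aim paragraph (SAP 1.1, Study objectives and endpoints; the same in Protocol 8.3, Objectives and Endpoints) states "we would like to confirm the decrease in cholesterol observed in our previous trial". The secondary objective in the table asks whether the product can "replicate the decrease in VLDL and total cholesterol we observed in our previous clinical trial". The same table cell also asks "Will the results from a controlled population translate to the iwi costumers".

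The matching endpoints are "Total Cholesterol change from baseline over 6-month period" and "VLDL-Cholesterol change from baseline over 6-month period". The table names no month-3 endpoint. The analysis paragraph (SAP 1.1, Study design; Protocol 9) does plan to compare baseline with both month 3 and month 6.

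The list of recorded variables has "calculated VLDL-cholesterol, triglycerides". Neither document gives the formula. SAP Table 2-2 lists VLDL with the laboratory parameters and does not mark it as derived.

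Protocol 8.3 (Background) describes the earlier study as a "double-blind, placebo-controlled, randomized three-month clinical trial". The present study is described in Protocol 9 and SAP 1.1 as open label with a single arm.

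**The concern.** To replicate or confirm a result, a study has to be able to reach the same kind of conclusion. The earlier design had a concurrent placebo group. Here the only contrast is follow-up against baseline, so a product effect cannot be separated from anything else that moves lipids over the same months.

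The plan itself gives reasons to expect such movement. Participants can monitor their own lipid results during the study (Protocol 8.3.2). Those with out-of-range results are directed to medical professionals or their GP, and some may leave the trial as a consequence (Protocol 10.4 and 10.6; SAP 2.8 and 2.10). Later kits are sent only after adherence is confirmed. Regression to the mean may add to this if people subscribe after a high reading, although the plan sets no lipid threshold for entry.

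The second difficulty is that one of the two markers named for replication is computed rather than measured. If it is computed from triglycerides, a single fall in triglycerides would be reported twice: as success on the primary endpoint and as replication of the VLDL result.

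**Working it through.** **1. The plan's own figures.** SAP 3 uses a two-independent-sample t-test on triglycerides with effect size 0.5, allocation ratio 1 and power 95%. That section gives no alpha, so two-sided 0.05 is taken from SAP 1.1. The normal formula gives n per group = 2(1.960 + 1.645)² / 0.5² ≈ 104, or 208 in total. The noncentral-t calculation gives 104.93, so 105 per group and 210 in total, with power 0.9501. The stated 210 is reproduced. It concerns triglycerides only; no figure is given for VLDL or total cholesterol. The Bonferroni threshold also checks: 0.05/20 = 0.0025.

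**2. What calculated VLDL adds.** As no formula is stated, two forms are assumed.

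- *VLDL = k × TG, with k > 0.* The change in VLDL is k times the change in TG. With mean change m and standard deviation s, t = km / (ks/√n) = m / (s/√n), so k cancels. It cancels in the Welch statistic in the same way, and ranks do not change. A simulated check with k = 1/5 and n = 210 gave a correlation of changes of 1.00 and the same p-values for TG and VLDL: 0.00348 (one-sample t on change), 0.290 (Welch) and 0.0856 (rank-sum).
- *VLDL = TC − HDL − LDL.* The mean change is the exact combination of three other listed mean changes. Its variance also depends on their covariances: V(TC) + V(HDL) + V(LDL) − 2C(TC,HDL) − 2C(TC,LDL) + 2C(HDL,LDL). The p-value is therefore its own. It cannot be read from the three component p-values, and it does not follow from the triglyceride result.

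The table lists eight outcomes: triglycerides, total cholesterol, VLDL, LDL, HDL, hs-CRP, glucose and HbA1c. Under either form at most 8 − 1 = 7 carry separate information.

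**3. What the missing control costs.** Assume 210 participants with paired values, no product effect, and a mean drift of δ standard deviations of the change. The noncentrality is δ√210 = 14.49δ. The probability that a two-sided paired t-test declares a change is:

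| Drift δ | Noncentrality | Alpha 0.05 | Alpha 0.0025 |
|---|---|---|---|
| 0.1 | 1.449 | 0.30 | 0.06 |
| 0.2 | 2.898 | 0.82 | 0.44 |
| 0.3 | 4.347 | 0.99 | 0.90 |

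The drift sizes are assumptions; the documents give none. The planned tests are two-sample. With within-person correlation r and equal variances, their noncentrality would be δ√(210(1 − r)), so for positive r these probabilities would be lower. The bias itself, a drift counted as an effect, would be the same.

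**4. Time point.** The earlier trial lasted three months. The endpoint table here gives six months, and the analysis text plans both. A comparison at the matching duration therefore exists in the plan, but nothing designates it as the one that addresses the replication objective.

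**The case against.** The strongest reply is that the design is openly stated. Both documents call the study open label and single arm, and Protocol 8.3.3 describes it as closer to a cohort study. The same objective cell asks about translation to customers, which is a fair question for such a study. The lack of a control affects every endpoint, and only a secondary objective is at issue here. All of this stands, and it limits the weight of the point. It does not justify *confirm* and *replicate*, which stand in the text beside the translation question.

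Several stronger readings are tempting, and the documents do not support them:

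- A reader might infer that the VLDL test certainly duplicates the primary test. That holds only under the proportional formula, and no formula is given.
- A reader might infer that the whole objective is redundant. Total cholesterol is a separate panel value; only the missing control and the undesignated time point affect it.
- A reader might infer that the plan ignores three months. The month-3 comparison is planned.
- A reader might infer that the plan promises independent confirmation. It does not use that term.
- A reader might infer that a redundant endpoint inflates false positives. Under Bonferroni, a perfectly correlated endpoint makes the correction more conservative. The harm lies in how results are counted and reported.
- A reader might infer that the trial says nothing about the earlier result. A clear absence of any decrease would still be relevant evidence, though weak.

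The documents also do not say how VLDL was obtained in the earlier trial or how large its effect was. No mismatch of method can be alleged, and no numerical benchmark can be set.

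**Conclusion.** The point holds as a limit on what may be concluded. A single-arm change from baseline cannot confirm or replicate a result from a randomized placebo-controlled trial, and calculated VLDL should not be counted as evidence separate from the lipids it is computed from.

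The size depends on stated assumptions. Drift alone, at 0.1 to 0.3 standard deviations of the change, would be declared significant with probability 0.30 to 0.99 at 0.05 and 0.06 to 0.90 at 0.0025, for a paired test with 210 participants. Identity of the VLDL and triglyceride tests requires the proportional formula. The weaker statement, that VLDL adds no separate measurement, holds under both assumed forms.

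This bears on a secondary claim and deserves correction. It leaves the primary endpoint and the sample size of 210 unaffected.

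**What to change.** Change the aim paragraph and the objectives table in both Protocol 8.3 (Objectives and Endpoints) and SAP 1.1 (Study objectives and endpoints):

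1. Replace *confirm* and *replicate* with an uncontrolled within-person change that is consistent, or not consistent, in direction with the earlier report, and state that no product effect is claimed from it. Only direction can be compared, because the documents give no earlier effect size. The translation question can stay under the same limit.
2. Name the already planned month-3 change in total cholesterol as the comparison matched to the earlier trial's duration, with month 6 as durability.
3. Keep VLDL if wanted, but label it as derived, state its formula, and do not count it as evidence separate from the lipids it is computed from. Mark it as derived in SAP Table 2-2 as well.

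The cost is wording and a weaker secondary claim. No new data are needed. Removing VLDL from formal testing is a further option, but a matter of judgement, since it is one of the two markers that the earlier trial reported.

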### 1.1. Study design

EPA is a type of omega-3 essential fatty acid known to play a beneficial role in protection against cardiovascular disease. Almega®PL is the only natural source containing EPA as sole n-3 HUFA that is available over the counter for human consumption. We **hypothesized** that AlmegaPL supplementation improves blood markers associated with heart health and inflammation. This post-market open label single armed trial involving 200-300 male and female participants, that will be monitored during the first 6 months following their subscription to Almega®PL.

As part of the **screening procedure**, participants will complete a short questionnaire to make sure they are new iwi users. Any participant who is already using iwi will not be considered in the study. Any participant that has a serious condition (including but not limited to kidney, neurological, immunological, liver, and gastrointestinal disease, any heart condition, or diabetes) will also be disqualified for the program and directed to their doctor. Any participant attempting conception, pregnant or breastfeeding will also be disqualified. All other participants will be accepted into the limited study based on their time of application until the quota is completed. Participation in this study is purely voluntary and participants can withdraw at any point without prejudice.

Participants will be asked to take the allocated product according to the **dose** prescribed (2 capsules per day containing 1000-1100 mg Almega®PL) and adherence to the protocol will be evaluated with a follow up email. Participants will be asked to maintain their usual level of physical activity and diet for the duration of the study. The dose used in this trial is in agreement with the commercial dose communicated to the FDA and comparable to doses previously used in our clinical trials.

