### 2.7. Analysis sets

### 2.7.1. Per protocol set (PPS)

The Per-Protocol Set (PPS) will consist of a subset of participants in the database who complete all 3 tests (baseline, month-3, and month-6 tests).

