### 2.7.2. Intention-To-Treat (ITT)

The Intention-To-Treat (ITT) will consist of a subset of participants in the database who complete at least 2 tests (baseline and month-3 test and/or month-6 test.

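### The set called ITT omits enrolled customers with no follow-up test, so the result describes adherent, tested, generally healthy new subscribers and not iwi customers in general

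*SAP*

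**What the plan says.** The overall aim, in protocol 8.3 (Objectives and Endpoints) and SAP 1.1, is effectiveness in "improving blood markers associated with heart health of iwi customers". One secondary question in the same table reads "Will the results from a controlled population translate to the iwi costumers". Neither sentence limits which customers are meant.

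The rules that decide who is analysed are these:

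- **Entry.** Protocol 9 and SAP 1.1 (Study design) admit new users only and disqualify "Any participant that has a serious condition (including but not limited to kidney, neurological, immunological, liver, and gastrointestinal disease, any heart condition, or diabetes"). People who are pregnant, breastfeeding or attempting conception are also excluded.
- **Baseline.** Under SAP 2.6, a participant whose baseline kit is not returned or is lost is discontinued.
- **Follow-up kits.** Participants are contacted at months 3 and 6, and "they will be sent subsequent kits once the confirmed adherence to the supplement".
- **Removal.** Under protocol 10.6 and SAP 2.10, a participant placed on cholesterol-lowering medication leaves the trial.
- **Analysis sets.** The ITT set of SAP 2.7.2 holds those "who complete at least 2 tests (baseline and month-3 test and/or month-6 test". The per-protocol set of SAP 2.7.1 holds those "who complete all 3 tests (baseline, month-3, and month-6 tests".

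The heading of SAP 2.9 begins with patient disposition, but its two subsections cover only health background and diagnosis or family history.

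**The concern.** Whether a result carries over to customers depends partly on how customers use the product, and stopping is part of that use. As written, someone who has stopped and does not confirm adherence is not sent the next kit. The missing tests are thus linked to product use by design, and someone who stops before month 3 has no route into the set called ITT.

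The label adds to the problem. A reader takes ITT to mean that people count whether or not they kept to the regimen. Here the set depends on confirmed adherence and a returned kit. No flow counts, missing-data method or comparison of tested with untested people is planned. A fall in triglycerides or cholesterol in this set could then be reported as an ITT finding for iwi customers, and the reader could not tell how many enrolled people it leaves out.

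**Working it through.** **1. The plan's own figure.** The documents state no retention or adherence figure. The only related number is the sample size in SAP 3: 210 in total, for a two-sample t-test with effect size 0.5, ratio 1 and power 95%. SAP 3 gives no alpha; at an assumed 0.05 two-sided, the noncentral t gives 105 per group, 210 in total, with power 0.9501. The figure reproduces, so the point does not rest on a sample-size error.

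**2. Who is in each set.**

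| Enrolled person | ITT (SAP 2.7.2) | Per protocol (SAP 2.7.1) | Planned count |
|---|---|---|---|
| No baseline result | out | out | none |
| Baseline only (stopped, did not respond, or kit not returned) | out | out | none |
| Baseline and month 3, then stopped | in | out | none |
| Baseline and month 6 only | in | out | none |
| All three tests | in | in | none |

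The second row is the gap. Protocol 10.4 and SAP 2.8 say that data collected before withdrawal will be used, yet a person with a baseline alone is in neither set. SAP 2.2 mentions participants who discontinued, but it fixes when the analysis takes place; SAP 2.7.2 defines membership. Protocol 9 names the per-protocol population for the analysis and SAP 1.1 names ITT. Both sets depend on returned kits, so neither closes the gap.

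**3. What the omission can do to the estimate.** Let D be the mean change in those tested, q the share of people with a baseline who are untested, and U the mean change in the untested, which is unobserved. Over everyone with a baseline:

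mean change = (1 − q) × D + q × U

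With U = 0 this is (1 − q) × D. The documents give no q, so the values below are assumptions. The third column applies the factor to the SAP's effect size of 0.5, with the SD held fixed. The last column applies it to the planned 200–300, taking all of them to have a baseline.

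| q (assumed) | Effect relative to that reported | 0.5 becomes | Tested of 200–300 |
|---|---|---|---|
| 10% | 0.9 | 0.45 | 180–270 |
| 20% | 0.8 | 0.40 | 160–240 |
| 30% | 0.7 | 0.35 | 140–210 |
| 50% | 0.5 | 0.25 | 100–150 |

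U = 0 is not a bound. If untested people worsened, the figure over everyone is smaller still; if they improved, it is larger.

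**4. Why the zero-change estimate should carry no test.** Take a paired analysis with a change of d SDs in the tested share r = 1 − q. Filling in zeros gives mean r × d and variance r × (1 + (1 − r) × d²). The test statistic, relative to that from the tested people alone, is then 1/√(1 + (1 − r) × d²). With d = 0.5 and r = 0.5 this is 1/√(1 + 0.5 × 0.25) = 1/√1.125 = 0.94. The estimate halves while the statistic falls by only about 6%, because the constants add almost no variance. A p value from it would look more robust than it is.

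**The case against.** The strongest reply is that the trial does study customers. Protocol 8.3.3 says participants would take the product anyway, and they buy it themselves. The primary and hs-CRP objectives already refer to a generally healthy population, and the title of the earlier trial in SAP 4 also refers to healthy individuals. The health exclusions therefore suit the population whose result is being carried over. This stands: the trial can describe change in generally healthy new customers who stay on the product and return tests. It does not stand for the aim and the secondary question, which name customers without that limit, or for the ITT label.

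The kit sentence could also be read as a matter of timing. But neither document gives a route to a kit for someone who does not confirm adherence.

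Three stronger readings are tempting, and the documents do not support them:

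- *That everyone who stops drops out of the analysis.* A person tested at month 3 who then stops stays in the ITT set, and data up to withdrawal are to be used. Only those with no baseline or no follow-up test are lost altogether.
- *That filling places in order of application biases the result.* This is ordinary enrolment to a quota; no mechanism or direction of bias follows from the text.
- *That the share of all customers represented can be worked out.* The documents give neither eligibility nor retention, so such a figure would only multiply guesses.

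It is also fair to say that zero-change imputation rescales the mean by the tested share and little more. That is why it belongs beside the counts as a point estimate and should not replace them.

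**Conclusion.** The point holds in this form: the population analysed is narrower than the one named in the aim and the secondary objective, the excluded enrolled people are not counted, and the ITT label hides this. The result describes generally healthy new subscribers who confirmed adherence and returned tests.

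The size is unknown from the documents. The factor (1 − q), or 0.9–0.5 for an assumed q of 10–50%, rests on no change in the untested and illustrates what the planned outputs cannot show.

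A reader might infer that the trial says nothing about carry-over to customers. That goes too far, since it informs the narrower group. Separately, there is no control arm, so change even in the tested group cannot be attributed to the product; rewording the population does not cure that.

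**What to change.** 1. **Objective.** In protocol 8.3 and SAP 1.1, restate the aim and the secondary question for *generally healthy new subscribers who confirm adherence and return tests*. Reconcile this with SAP 2.9.2, which plans percentages with cardiovascular disease and diabetes although any heart condition and diabetes are disqualifying at screening.
2. **Set names.** Rename the two-test set, for example *evaluable set*, and reserve ITT for all enrolled people with a baseline. Align the analysis population named in protocol 9 with the SAP.
3. **Flow.** Under SAP 2.9, report the numbers screened out, enrolled, with a baseline, confirming adherence and tested at months 3 and 6. Give baseline values for tested against untested people.
4. **Sensitivity.** Beside the main estimate, give one estimate over all enrolled people with a baseline, with untested people set to zero change. Present it as a point estimate only, without a significance test and without calling it a bound.

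None of this needs extra visits, assays or participants. The flow table should be built from the study's own screening, contact and kit records, because the documents do not say that subscription records can be linked to test data. The sponsor is to receive aggregated data, so items 3 and 4 require those data to include baseline values for people not retested. The downside is a narrower claim and a less favourable second figure.

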## 4-Mar-2022

### 2.2. Data included in the analysis

The study data will be analyzed and reported based on all patient's data when all participants have completed at least 2 tests or discontinued the study (ITT population).

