### 2.10. Termination of the Study

This research project may be stopped for a variety of reasons.

During the trial, any participant that records out-of-range analytical levels will be referred to their GP for assessment of suitability/safety for continuation in the trial.

At the discretion of the GP the participant will either be placed on standard care of cholesterol-lowering medication (and removed from the trial) or continue in the trial on the supplementation.

The participant also has the option to stop supplementation at any point.

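### hs-CRP values raised by a passing illness enter the change from baseline unflagged, which mainly weakens the planned mean-based analyses

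*SAP*

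**What the plan says.** Lowering hs-CRP is a stated secondary objective (Protocol 8.3 Objectives and Endpoints; SAP 1.1 Study objectives and endpoints). The endpoint is "hs-CRP change from baseline over 6-month period", with no scale, cut-off or repeat test.

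- **Sampling** (SAP 1.1 Study design): levels are followed "across a supplementation period (baseline, month 3 and month 6) thanks to a finger prick blood drawing system". After baseline, participants are contacted and "they will be sent subsequent kits once the confirmed adherence to the supplement". No health check before sampling is described.
- **Screening** (same section): the health exclusion is for serious conditions. An ordinary acute illness is not named.
- **Analysis sets**: the ITT set is "a subset of participants in the database who complete at least 2 tests" (SAP 2.7.2), and the per-protocol set requires all three tests (SAP 2.7.1). SAP 2.2 adds: "The study data will be analyzed and reported based on all patient's data when all participants have completed at least 2 tests".
- **Out-of-range results** (SAP 2.10): "any participant that records out-of-range analytical levels will be referred to their GP for assessment of suitability/safety for continuation in the trial". This concerns participant care and does not say whether the value is analysed.
- **Adverse events** (SAP 2.11): they are to be documented, with no link to sampling dates.
- **Tests** (SAP 1.1 Study design): the "population will be first tested for normality before any other test will be conducted". Then comes a Welch t-test or a Wilcoxon rank-sum test, two-tailed, and an ANCOVA adjusting for baseline as well. The significance level is 0.05, Bonferroni-adjusted to 0.0025 for 20 outcomes.
- **Summaries** (SAP 2.3): quantitative data are described by mean, SD, median, minimum and maximum.

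**The concern.** The objective is about a persistent level of inflammation. The argument assumes, as the documents do not discuss, that an infection or injury can raise hs-CRP several-fold for a short time. With home sampling, some kits will be used during such an episode, and nothing in the plan then separates that value from the participant's usual level.

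A few very high values add far more variance to a mean change than their number suggests. At stake is whether a real modest fall would be detected, and whether the reported means and SDs describe the usual state of the participants. Recent illness is hard to recover after sampling. A rule for high values written once results are visible would be open to bias, and sponsor personnel do the analysis (SAP 2.1).

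**Working it through.** **1. The plan's own figure.** SAP 3 gives 210 for an effect size of 0.5, ratio 1 and 95% power. The normal approximation is 2(1.960 + 1.645)²/0.5² = 104 per group, 208 in total. The noncentral t gives 105 per group, 210. The figure reproduces at two-sided 0.05, but it is for triglycerides. No hs-CRP effect, SD or power is given.

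**2. Assumptions, none from the documents.** True fall 15% (|ln 0.85| = 0.1625); log SD 1.0; within-person correlation 0.75; 210 pairs; a fraction p of samples at each visit multiplied by 12 (ln 12 = 2.485, squared 6.175).

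**3. Paired log analysis** (not planned; used as a benchmark). The variance of the log change is V = 2(1 − 0.75) + 2p(1 − p)(6.175), and power ≈ Φ(0.1625/√(V/n) − 1.960).

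- No illness: V = 0.50, n = 210; 0.1625/0.0488 = 3.33; Φ(1.37) = 0.91.
- p = 5%: V = 0.50 + 0.587 = 1.087; 0.1625/0.0719 = 2.26; Φ(0.30) = 0.62.
- p = 5%, ill pairs perfectly excluded: n = 210 × 0.95² = 189.5; 0.1625/0.0514 = 3.16; Φ(1.20) = 0.89.
- p = 5%, self-report with 70% sensitivity and 5% false positives (assumed): flagged per sample 0.05 × 0.70 + 0.95 × 0.05 = 0.0825; n = 210 × 0.9175² = 176.8; ill among kept samples 0.05 × 0.30/0.9175 = 0.0163; V = 0.698; 0.1625/0.0628 = 2.59; Φ(0.63) = 0.73.

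Simulation agrees within about two points (0.90–0.91, 0.61–0.63, 0.87–0.88 and 0.73). Simulated power is about 0.76 at 2% ill and 0.49–0.52 at 8%.

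**4. Planned rank-sum test.** An unpaired comparison of logs is a close stand-in. It uses a standard error of √(2/210) = 0.0976, while the true one is 0.0488, half as large. Power ≈ Φ((0.1625/0.0976 − 1.960)/0.5) = Φ(−0.59) = 0.28 without illness. Simulated rank-sum power is 0.23–0.29 without illness, 0.22–0.24 at 5% ill, and 0.22 after dropping ill pairs. In every simulated trial checked, Shapiro-Wilk rejected normality of the baseline values, so this is the test the plan would reach.

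**5. Planned mean-based analyses, untransformed.** With an assumed median of 1.5 mg/L, the clean mean is 1.5e^0.5 = 2.47 and the SD is 2.47√(e − 1) = 3.24. At 5% ill, the mean is multiplied by 0.95 + 0.05 × 12 = 1.55 and the second moment (16.63) by 0.95 + 0.05 × 144 = 8.15. The SD becomes √(135.5 − 14.7) = 11.0. Simulated raw paired-t power falls from 0.59 to 0.10.

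The SAP does not say which term the single-arm ANCOVA tests. Taken as the mean change at the average baseline, its power falls from about 0.71 to 0.37, and is 0.67 with perfect exclusion. That test treats the observed baseline mean as fixed, so these levels are flattering; the drop matters more than the level.

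**6. At 0.0025** (0.05/20; critical value 3.023). The paired log analysis gives Φ(3.33 − 3.02) = 0.62 without illness, Φ(2.26 − 3.02) = 0.22 at 5% ill, 0.56 with perfect exclusion and 0.33 with imperfect recall. Rank-sum is about 0.01 or less throughout.

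**7. Other assumptions.** Take correlation 0.6, illness adding a median of 10–40 mg/L in 2–5% of samples, and alpha 0.05.

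| Test | 20% fall: clean | 20% fall: with illness | 30% fall: clean | 30% fall: with illness |
|---|---|---|---|---|
| Welch t, raw | about 0.40 | 0.06–0.30 | about 0.88 | 0.09–0.61 |
| Paired t, raw | about 0.70 | 0.06–0.45 | 0.96 | 0.09–0.73 |
| Rank-sum | 0.68 | 0.52–0.63 | 0.99 | 0.95–0.99 |

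**The case against.** The strongest reply is that the SAP already protects itself: hs-CRP is skewed, the normality check would lead to the rank-sum test, and ranks limit the pull of extreme values. That is right and sets the limit of the point. A reader might infer that illness removes most of the power of the planned hs-CRP test. The documents do not support that. The rank-sum loss is a few points in steps 4 and 7, at most about 16 at 2–5% illness, and excluding ill pairs gains that test nothing under the step 2 assumptions. Its low power for a 15% fall comes from ignoring pairing, and at 0.0025 from the threshold. The reply does not cover the ANCOVA, which is run whatever the normality result and has no stated transformation, or the means and SDs.

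A reader might also infer that a chance imbalance in illness between visits would create a false effect. Random illness at equal rates is already covered by the test's error rate. Only a systematic difference, such as season, would bias a single-arm comparison, and the documents give no basis for assuming one.

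Two further replies stand in part. The illness rate, size of rise, SD, correlation and effect are all assumed. And the screening questionnaire, kit instructions or adverse event records might touch on recent illness, since their full content is not shown. Even so, the SAP has no rule that would use such information for hs-CRP.

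**Conclusion.** The gap is real, but its reach is limited. hs-CRP values raised by a passing illness go into the analysis unflagged, and this bears mainly on an untransformed ANCOVA, any Welch t-test, and the means and SDs. Under the step 2 assumptions at 0.05, the ANCOVA loses about 34 points (0.71 to 0.37) and the rank-sum test almost nothing. A better, paired log analysis would also lose power, about 0.91 to 0.62, so the matter remains once pairing is corrected. Exclusion would recover most of that only if illness were reported perfectly; with plausible misreporting it recovers about a third (0.62 to 0.73). The direction is firm and the sizes are not, because no hs-CRP input is in the documents. This is a low-cost improvement to a secondary endpoint and does not touch the triglyceride result.

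**What to change.** 1. In the SAP, make the hs-CRP analysis the within-person change on the log scale, in all pairs, by paired t-test or signed-rank test. If the ANCOVA is kept, run it on log values and state which term is tested.
2. At each of the three samplings, ask one yes/no question about recent infection, fever, injury or procedure, over a fixed look-back such as 14 days.
3. Before any hs-CRP result is seen, pre-specify a supporting analysis restricted to pairs answered 'no' at both visits, reported beside the all-pairs result and not in place of it. Other analytes keep all pairs.

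The cost is one question per kit and a short SAP paragraph. At 5% ill per visit, 1 − 0.95² = 9.75% of pairs leave the supporting analysis under perfect reporting, and 1 − 0.9175² = 15.8% under the misreporting assumed above. Self-report will misclassify some samples, and the restriction depends partly on status after baseline, which is why it should stay supporting.
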